5.3.2. Titration of Nevanimibe HCl Dose

At Visit T2 (Day 29), all subjects will have their nevanimibe HCl dose up-titrated from 500 mg BID to 1000 mg BID and will also have serum 17-OHP levels obtained. Based on the results of the Visit T2 serum 17-OHP level (expected to be available prior to Day 43, the start of Week 7), if the primary endpoint was not achieved on the nevanimibe HCl 500 mg BID dose, the subject will continue on 1000 mg BID (for Weeks 7-8; Days 43-56) and automatically up-titrate to 1500 mg BID for Weeks 9-10, Days 57-70. If the primary endpoint was achieved, appropriate study site personnel will contact the subject via telephone prior to Day 43 to instruct them on down-titrating their nevanimibe HCl dose from 1000 mg BID to 500 mg BID (for Weeks 7-10; Days 43-70). Note: subjects should change to their updated dose the day they are contacted by the site to do so; they do not need to wait until Day 43 to start the updated dose. The primary endpoint is defined as follows:

- Men and postmenopausal women: $17\text{-OHP} \leq 2x \text{ ULN}$
- Premenopausal women:
 - Follicular phase: $17\text{-OHP} \leq 2x \text{ follicular phase ULN}$
 - Luteal phase: $17\text{-OHP} \leq (2x \text{ follicular phase ULN} + (\text{luteal phase ULN} - \text{follicular phase ULN}))$

At Visits T3 (Day 57) and T4 (Day 85), all subjects will again have their serum 17-OHP levels obtained. The serum 17-OHP samples require ~10 days to process. When the predose serum 17-OHP results are available following Visits T3 and T4, appropriate study site personnel will contact the subjects via telephone to instruct them on any potential dose adjustments:

- Subjects whose predose serum 17-OHP is $\leq 2x$ ULN (primary endpoint is met) will have their nevanimibe HCl dose decreased to the dose on which they most recently met the endpoint if they underwent a dose increase at their most recent treatment period site visit.
- Subjects whose predose serum 17-OHP is $> 2x$ ULN (primary endpoint is not met) will have their nevanimibe HCl dose increased to the next higher dose level if they did not already undergo a dose increase at their most recent treatment period site visit.
- All other subjects will remain on their current nevanimibe HCl dose.

Note: subjects should change to their updated dose the day they are contacted by the site to do so; they do not need to wait until 14 days after their scheduled treatment period site visit to start the updated dose.

5.3.3. Drug Holidays and Down-Titration

During the Treatment Period, the nevanimibe HCl dose may be down-titrated and/or a “drug holiday” taken at any time (independent of study visit schedule) for safety-related reasons. However, such events should be discussed with the Medical Monitor ahead of time, whenever feasible, or after the fact to align on the treatment regimen/plan moving forward.

5.3.4. Missed Doses

If a subject forgets to take a nevanimibe HCl dose on a given day (e.g., the AM dose was not taken), a “make up” dose should not be taken. In general, if more than 4 hours have passed beyond the usual time of day when the dose is taken, that particular dose should not be taken.

5.3.5. Compliance

The study drug is to be dispensed by qualified personnel at the study site and only to subjects enrolled in the study. Subject compliance to therapy will be assessed at scheduled study visits by counting the number of tablets returned. Treatment compliance is defined as the subject taking 80% to 120% of the study tablets to be taken during the dosing period for a given dose level. Subjects found to be outside of the definition of compliance may be discontinued from the study at the discretion of the Investigator.

5.3.6. Blinding

This is an open-label study. Neither Investigators nor subjects will be blinded to treatment.

5.4. Study Drug Packaging and Labeling

The formulation and bulk packaging of nevanimibe HCl will be conducted according to standard procedures. The drug product will be packaged and labeled by Millendo Therapeutics US, Inc.’s designated contract packager and labeler according to regulatory requirements.

5.5. Study Drug Storage and Accountability

Study drug must be kept in a secure location and stored at controlled room temperature at the study site within its original container. A daily temperature log for monitoring of proper storage conditions must be maintained by the site.

Access to drug must be restricted to designated study personnel only. Under no circumstances should the Investigator or site personnel supply study product to other Investigators or clinics, or allow the supplies to be used other than as directed by this protocol, without written authorization from the Sponsor. The Investigator (or designee) must maintain records of the delivery of the study drug to the study site, the inventory at the site, use for each subject, and return of the study drug to the Sponsor (or designee) or destruction. Total study site accountability will be conducted at the end of the study and the Investigator (or designee) must explain all discrepancies. A Site Drug Accountability Log will be supplied by the Sponsor. This log must be kept current and should contain the following information:

- Identification (subject ID) of the subject to whom the study drug was dispensed
- The dates the study drug was dispensed
- Initial inventory on receipt of drug at the site
- Final inventory on completion of the study

All records and inventory must be available for inspection by the clinical study monitor. Additional details on the storage and handling of nevanimibe HCl will be provided in the Pharmacy Manual.

5.6. Investigational Product Retention at the Study Site

At the time of study close-out, the Sponsor will direct the site regarding the disposition of any unused study drug, whether it is to be destroyed or be returned to the Sponsor's designated location. The Sponsor will assure that a final report of drug accountability is prepared and maintained by the investigative site. Additional details on the inventory of study drug will be provided in the Pharmacy Manual.

5.7. Concomitant Medications

Use of concomitant medications should be kept to a minimum during the study. However, if concomitant medications are considered necessary for subject welfare, they may be given at the discretion of the Investigator. During the study, any medication given other than the study drug (including blood transfusions, parenteral fluids, over-the-counter medications, and herbal preparations) is to be considered a concomitant medication and must be documented on the eCRF. See [Section 6.5](#) for additional details regarding documentation of prior and concomitant medications.

Glucocorticoid and mineralocorticoid replacement are critical concomitant medications used in classic CAH. Subjects must continue to receive glucocorticoid and mineralocorticoid (if applicable) according to their individual regimens established prior to enrolling in the study. Other than as specified in Appendix 2, the regimen should remain as stable and unchanged as possible to minimize potential confounding effects on efficacy outcome measures. However, changes are permitted to ensure subject safety. It is not expected that nevanimibe HCl will result

in a need for increased doses of glucocorticoid replacement, as the glucocorticoid synthetic pathway is already compromised in classic CAH. Therefore, decreasing cortisol precursors (i.e., 17-OHP) should not result in increased glucocorticoid requirements over the treatment period.

The timing of glucocorticoid replacement therapy may have an impact on the measurement of 17-OHP. Consequently, on clinic days when blood and/or saliva samples for adrenal steroids/steroid intermediates are to be collected, the morning dose of replacement steroids (glucocorticoid and mineralocorticoid) must not be taken until after the sample collection as this could confound efficacy endpoint measures. Glucocorticoid and mineralocorticoid replacement doses should be taken after samples are obtained for laboratory assessments. Similarly, when subjects collect salivary 17-OHP profiles at home, the first (~8 AM/08:00) sample should be obtained prior to the morning dose of replacement steroids. See Section 6.11 for additional details on the timing of blood and saliva samples.

Approximately 75% of classic CAH subjects have deficiency in the mineralocorticoid pathway in addition to the glucocorticoid pathway (Auchus, 2010). Thus, the majority of subjects in this study are anticipated to be on mineralocorticoid replacement. Nevanimibe HCl inhibition of the mineralocorticoid pathway for these subjects should not have an effect on mineralocorticoid replacement therapy. Subjects who enter the study with sufficiently intact endogenous mineralocorticoid production may be impacted by suppression of this pathway by nevanimibe HCl. Pharmacological doses of glucocorticoids, especially shorter acting ones such as hydrocortisone, also confer mineralocorticoid activity and the need for additional replacement mineralocorticoid is not always required (Speiser, 2010). However, mineralocorticoid replacement should be initiated as soon as possible if there is suspicion of insufficiency.

5.8. Prohibited and Restricted Medications

Nevanimibe HCl is most soluble in acidic conditions. Proton pump inhibitors are prohibited and calcium preparations and antacids should not be used 2 hours before to 2 hours after nevanimibe HCl administration.

Concurrent use of medications that are known to prolong the QT/QTc interval at therapeutic exposures and those that only cause prolonged QT intervals in unusual circumstances (e.g., overdosage) may be used with caution (Appendix 4, Lists A, B and C).

Nevanimibe is metabolized by CYP3A4 and is a moderate inhibitor of CYP3A4. As a consequence, nevanimibe may interfere with the metabolism of other medicines that are metabolized by CYP3A4. In addition, the metabolism of nevanimibe may be affected by other medicines or foods such as grapefruit products that inhibit CYP3A4; thus, grapefruit products should be avoided. Drugs known to be metabolized by CYP3A4 are shown in Appendix 5 and should be used with caution if they are known to interact with weak or moderate CYP3A4 inhibitors.

Nevanimibe may be an inhibitor of P-glycoprotein and OATP1B1. *In vitro* data indicate that nevanimibe may compete with certain drugs for P-glycoprotein in the intestinal lumen. Consequently, the drugs listed in Appendix 6 should be used with caution, as they may impact nevanimibe exposure or vice versa. Note that some of these drugs may also appear in Appendices 3 or 4.

5.9. Precautions and Warnings

Preclinical studies have identified adrenal suppression with apoptotic histologic changes with nevanimibe HCl dosing. Such changes were associated with exposure levels higher than those anticipated for this study. However, occurrence of such changes is a possibility. The investigative staff should be familiar with the warnings and precautions for nevanimibe HCl as presented in the ATR-101 (nevanimibe HCl) Investigator's Brochure.

6. STUDY ASSESSMENTS

6.1. Allowable Variation in Time of Procedures

The indicated study days for assessments are intended as targets and variations may be made to allow for logistical considerations and to accommodate scheduling conflicts. Unless otherwise specified in this protocol, study procedures and visits during the Treatment Period have a window of ± 2 days. Study procedures and visits during the Screening, Baseline, and Follow-up Periods have a window of ± 7 days, although up to ~ 14 weeks may be allowed for Screening and up to ~ 8 weeks may be allowed for Baseline (e.g., for additional glucocorticoid dose adjustment or stabilization of Cohort 2 subjects—see Appendix 2) with approval of the Medical Monitor. If a study visit occurs early or late, the timing of subsequent visits may be re-anchored.

6.2. Informed Consent

Prior to any study specific screening evaluations and clinical trial participation, written informed consent will be obtained from each subject to be involved in the clinical trial by using the Institutional Review Board (IRB)/Ethics Committee (EC)-approved ICF. Potential subjects will be informed in detail about the study drug and the nature of the clinical investigation with the risks and discomforts to be expected. The subjects will also be instructed that they are free to withdraw their consent and discontinue their participation in the clinical study at any time. The Investigator or qualified designee will verify that the subject has granted consent. Each subject will be given a copy of the signed ICF. Certified translated ICFs will be provided by the Sponsor in those languages required or requested by investigational sites.

6.3. Eligibility

Review of all assessable study inclusion/exclusion criteria will be done at/after the Screening visit (Visit S1) and before enrolling the subject at Visit T1.

6.4. Medical History

A complete medical history will be obtained at the Screening visit (Visit S1). The following systems will be reviewed: head, eyes, ears, nose and throat (HEENT), respiratory, cardiovascular, gastrointestinal/hepatobiliary (specifically, a history of liver dysfunction or the presence of hepatomegaly or splenomegaly), genitourinary/ reproductive, musculoskeletal, neurological, psychiatric, endocrine/metabolic, blood/lymphatic, dermatologic and immunologic. Past surgeries will also be recorded.

6.5. Prior and/or Concomitant Medication Assessments

Prior and concomitant medications that should be recorded include any treatments taken from Screening (Visit S1) until the end of the study (F1/End-of-Study (EoS) visit), as well as any replacement glucocorticoids and mineralocorticoids taken during the 4 weeks prior to Screening. Glucocorticoid and mineralocorticoid replacement are critical concomitant medications used in classic CAH and will be captured on a separate eCRF from other concomitant therapies. Any other treatments given during the study other than nevanimibe HCl, including blood transfusions, parenteral fluids, over-the-counter medications, and herbal preparations, are also considered to be concomitant therapies and must be recorded on the concomitant medications eCRF.

6.6. Electronic Diary

At Visit B1, subjects will be instructed in the use of the eDiary for recording glucocorticoid, mineralocorticoid, and/or study drug doses. Premenopausal women will also be instructed in the use of the eDiary for recording the start dates of their menstrual periods. The eDiary entries will be used to help assess compliance with glucocorticoid and study drug dosing and, in premenopausal women, they will be used to help assess menstrual cycle phase. The eDiary may also be used to provide reminders to subjects.

6.7. Vital Signs, Height, Weight and Body Mass Index

Vital signs (temperature, systolic and diastolic blood pressure, pulse and respiratory rate) and weight will be measured throughout the study.

Systolic and diastolic blood pressure should be taken in the same arm per subject after the subject has been sitting for at least 5 minutes. Any clinically necessary deviations to this will be documented but do not need to be confirmed with the Medical Monitor prior to occurrence and do not need to be documented as protocol deviations.

Body weight will be obtained at each study visit. Height will be assessed only at Screening. Body mass index will be calculated based on body weight and height.

6.8. Physical Examination

A complete PE will be obtained at Visits S1, T1, and T5/EoT. A brief PE will be performed at Visits T2, T3, T4, and F1/EoS, with particular attention to assessing the subjects for adrenal insufficiency. At any time, targeted PEs may be performed if needed based on adverse events and positives from review of systems.

The following systems will be examined for a complete physical examination: HEENT, respiratory, cardiovascular, gastrointestinal/hepatobiliary (specifically the presence of hepatomegaly or splenomegaly will be assessed), musculoskeletal, neurological, dermatologic, and any areas pertinent to any adverse events (AEs) and positives from review of systems. On a brief PE, the following systems will be examined: respiratory, cardiovascular, gastrointestinal/hepatobiliary and any areas pertinent to any adverse events and positives from review of systems.

6.9. Electrocardiography and Determination of QTc

All subjects will have 12-lead ECGs performed at Visits S1 and T5/EoT. The ECG test tracings will be interpreted by usual clinic procedures, and ECG findings will be recorded on the eCRF. ECGs will be stored for later analysis if needed.

If the QTc interval is greater than 470 (450 in France) msec on the Screening (Visit S1) ECG, three consecutive ECGs will be obtained and the QTc values corrected by the Fridericia method will be averaged. If the average is greater than 470 (450 in France) msec, the subject will be ineligible for the study.

For all ECGs, the QT interval will be corrected using the Fridericia method ($QTcF = QT/RR^{0.33}$). During the study, if the QTcF is greater than 470 (450 in France) msec, a repeat 12-lead ECG will be obtained as soon as practicable.

In the event of an abnormal ECG (especially in the setting of an intraventricular conduction delay) that makes QTc interval determination unreliable by standard means, the QT interval will be corrected by the method of Rautaharju et al. (Zhou, 1992; Rautaharju, 2004).

6.10. Adverse Events, Serious Adverse Events and Reporting

6.10.1. Definition of Adverse Event, Adverse Drug Reaction and Unexpected Adverse Drug Reaction

Adverse Event (AE): Any untoward medical occurrence associated with the use of a drug in humans, whether or not considered drug-related.

- All AEs, regardless of relationship to study drug, should be collected beginning from the time the subject signs the informed consent form until the last study visit or 30 days after the last dose of study drug, whichever is later. (Any serious adverse event (SAE) judged by the Investigator to be related to the study treatment should be reported to the Sponsor regardless of the length of time that has passed since study completion.) AEs in study subjects include any change in the subject's condition. This includes symptoms, physical findings, or clinical syndromes.
- Wherever possible, a specific disease or syndrome, rather than individual associated signs and symptoms, should be identified by the Investigator and recorded. However, if an observed or reported sign or symptom is not considered a component of a specific disease or syndrome by the Investigator, it should be recorded as a separate AE. Additionally, the condition that led to a medical or surgical procedure (e.g., surgery, endoscopy, tooth extraction, or transfusion) should be recorded as an AE, not the procedure. Any medical condition already present at screening should not be reported as an AE unless the medical condition or signs or symptoms present at baseline worsens in severity or seriousness at any time during the study. Clinically significant examination (e.g., electrocardiogram) findings that are detected during the study or are present at screening and worsen during the study should be reported as an AE.
 - An abnormal laboratory value may be considered an AE if the identified laboratory abnormality leads to any type of intervention, whether prescribed in the protocol or not. It is up to the Investigator to determine whether an abnormal laboratory value constitutes an AE. If an abnormal laboratory value is caused by a disease process, the disease process and not the laboratory abnormality should be listed as the AE (e.g., if new onset viral hepatitis is causing elevated ALT, the specific hepatitis and not the elevated ALT should be listed as the AE).
 - Examples of laboratory abnormalities that should be considered AEs include those that result in withdrawal of the study treatment or additional concomitant treatment. All laboratory abnormalities considered to constitute an AE should be recorded on the appropriate AE page of the eCRF. Laboratory abnormalities do not need to be listed as separate AEs if they are considered to be part of a clinical syndrome that is being reported as an AE. It is the responsibility of the Investigator to review all safety laboratory findings in all subjects. Abnormal values should be commented upon as to clinical relevance or importance on the eCRF or the laboratory report as appropriate.

Medical and scientific judgment should be exercised in deciding whether an isolated laboratory abnormality should be classified as an AE.

- Every effort must be made by the Investigator to categorize each AE according to its severity and its relationship to study drug.
- Subjects who develop toxicity on study will be followed until the event resolves, stabilizes or returns to baseline.

Adverse Reaction: All noxious and unintended responses to study drug at any dose should be considered to be adverse reactions. “Responses to study drug” means that there is a causal relationship between the study drug and the responses. “*Suspected* adverse reaction” implies a lesser degree of certainty about causality than “adverse reaction.”

Unexpected Adverse Reaction: An unexpected adverse reaction is defined as an adverse reaction, the nature or severity of which is not consistent with the applicable product information. For the study drug, the reference safety information is included in the version of the ATR-101 (nevanimibe HCl) [Investigator's Brochure](#) currently in force.

6.10.2. Assessing Severity of Adverse Events

The assessment of severity must be provided by the Investigator and based on the Investigator’s clinical judgment. Maximum severity should be assigned to one of the following categories:

- Mild: An AE that is easily tolerated by the subject, causing minimal discomfort and not interfering with everyday activities.
- Moderate: An AE that is sufficiently discomforting to interfere with normal everyday activities.
- Severe: An AE that prevents normal everyday activities.

An AE that is assessed as severe should not be confused with an SAE. Refer to [Section 6.10.4.1](#) for the definition of an SAE.

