9.6.2. Safety Analyses

No inferential statistical analyses will be performed on the safety data from this study. The Safety Population will be used for all summaries of safety data. Only observed case data will be used. The summarization of AEs will include treatment-emergent AEs (TEAEs; defined as AEs that begin or worsen after the first dose of study drug). TEAEs and treatment-emergent SAEs (TESAEs) will be summarized by MedDRA system organ class (SOC) and preferred term (PT), severity, and relationship to study drug, overall, by nevanimibe HCl dose, and by cohort. Deaths and discontinuations due to AEs will each be summarized, overall, by nevanimibe HCl dose, and by cohort. Clinical safety laboratory results, PE findings, vital signs, and ECG readings will be summarized by value and by change from baseline in the value, where appropriate, for each time point, overall, by nevanimibe HCl dose, and by cohort using summary statistics for continuous parameters, including number of non-missing observations (n), mean and/or median, standard deviation (SD) and/or percentiles, minimum (min), and maximum (max). Frequencies and percentages as well as shift tables will be prepared for categorical parameters.

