2.5 Study Hypothesis

The hypotheses to be investigated by this study include whether sustained, continuous dosing of nevanimibe HCl will result in greater efficacy than observed in the previous Phase 2 CAH study (ATR-101-201) and whether higher doses are needed. Additionally, it will be evaluated whether the higher doses used in this study still have a sufficient safety profile. The primary efficacy endpoint will be evaluated by means of the percentage of subjects achieving predose serum 17-OHP targets as follows:

- Men and postmenopausal women: 17-OHP $\leq 2 \times$ ULN
- Premenopausal women in follicular phase: 17-OHP $\leq 2 \times$ follicular phase ULN
- Premenopausal women in luteal phase: 17-OHP $\leq (2 \times \text{follicular phase ULN} + (\text{luteal phase ULN} - \text{follicular phase ULN}))$

The responder rate (percentage of subjects achieving the predose serum 17-OHP targets) for Cohort i ($i=1, 2$) will be calculated as follows:

$$\text{Responder rate}_{Ci} = \frac{\text{Number of responders in } Ci}{N_{Ci}} \times 100\%$$

with Ci being the corresponding cohort. The responder rate will also be calculated overall.

The study will be considered positive if 40% or more of enrolled subjects in either cohort were classified as responders at any of the four visits T2 (Day 29), T3 (Day 57), T4 (Day 85) or T5 (Day 113; Amendment 2).

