7.3 Calculation of Study Days and Durations

Study days and, if applicable and meaningful, durations will be determined by comparing the respective date to the date of first dose of study drug.

- If the respective date is on or after date of first dose of study drug:
$$\text{Study day/Duration} = (\text{Date (e.g., date of visit)} - \text{Date of first dose of study drug}) + 1$$
- If the respective date precedes the date of first dose of study drug:

Study day/Duration = Date (e.g., date of medical history event) - Date of first dose of study drug

Time to onset and duration of adverse events will be calculated as follows:

- Time to onset = start date of AE - date of first dose of study drug [+1 for AE starting on or after date of first dose of study drug]
- Duration of adverse event = (stop date - start date) + 1

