7.7 Evaluation of Safety Endpoints

All safety variables will be evaluated for the safety population (SP). The analyses of treatment-emergent adverse events (TEAEs) will be performed overall and for subjects enrolled under global

amendment 1 and global amendment 2 separately. The analysis on the SOC and PT level will be repeated for the All Screened population to cover all AEs, also those recorded prior to first treatment with the study drug.

Treatment-emergent adverse events (TEAEs) will be summarized overall and by causal relationship and severity. TEAEs will be coded using the latest MedDRA version at the time of database close. Incidences and percentages will be provided on the subject-level (n), overall as well as on the system organ class (SOC) level and on the preferred term (PT) level for all subjects and by nevanimibe dose category. Results will additionally be prepared by time range. The suitable time ranges will be selected during the DRM for Cohort 1. A subject with more than one AE overall or assigned to one SOC or assigned to one PT will be counted once for the worst category (causal relationship or severity) on the subject level. For the summarization by relationship to study drug, the relationship will be categorized as “related” and “not related,” where related AEs are those with at least a possible relationship to the study treatment. For the summarization by nevanimibe dose, subjects with more than one AE overall or assigned to one SOC or assigned to one PT will be counted once on the subject level at the lowest nevanimibe dose category on which they experience the AE (i.e., a subject with two AEs, one when treated with 1000 mg BID and one when treated with 1500 mg BID, will be counted once at the 1000 mg BID dose). Additionally, the number of AEs per patient-year of treatment will be calculated by nevanimibe dose as (sum of number of AEs of subjects at the respective nevanimibe dose) / (patient-years of treatment at the respective nevanimibe dose).

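### Severity reached after a dose increase can be tabulated at the lower dose, and no rule says how worsening of an ongoing adverse event is recorded

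*Protocol*

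**What the plan says.** - **Severity.** Protocol 6.10.2 gives three grades and one instruction: "Maximum severity should be assigned to one of the following categories". No section asks when that maximum was reached, or on which dose.
- **Dates.** SAP 7.3 works from the start and stop dates only: "Time to onset = start date of AE - date of first dose of study drug" (one day is added for events on or after the first dose) and "Duration of adverse event = (stop date - start date) + 1".
- **Treatment emergence.** Protocol 9.6.2 describes treatment-emergent AEs as "defined as AEs that begin or worsen after the first dose of study drug". SAP 7.7 uses the term without defining it. Under Protocol 6.10.1, AEs "should be collected beginning from the time the subject signs the informed consent form", so an AE can start before dosing.
- **Counting.** In SAP 7.7, a subject with more than one AE (overall, in a system organ class or in a preferred term) is placed once in the worst severity category. By dose, such a subject "will be counted once on the subject level at the lowest nevanimibe dose category on which they experience the AE".
- **Tables.** SAP Appendix 1 lists Tables 14.3.1.4 (all treatment-emergent AEs) and 14.3.1.6 (drug-related ones), both by dose level and maximum severity.
- **Purpose.** SAP 2.5 states that "it will be evaluated whether the higher doses used in this study still have a sufficient safety profile".

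**The concern.** Each subject moves through several doses. Protocol 3.1.3 raises everyone at Visit T2 and raises non-responders again at T3 and T4. Only two of ten subjects reached target in the previous Phase 2 study (Protocol 3.2), so repeated escalation may be common. An event that begins mildly and intensifies as the dose rises is a pattern this design ought to be able to show. Gastrointestinal events are a plausible case: Protocol Appendix 7 links such effects to tablet number, and Protocol Table 2 goes from one to four tablets per dose.

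If an event is described by its onset date and its peak severity, the dose at onset is joined to a severity that may belong to a later, higher dose. In an upward titration that error runs one way: it moves severity from higher doses to lower ones, in the tables a reader would use to answer the question in SAP 2.5.

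The second issue is treatment emergence. The protocol's definition depends on worsening, so it needs a date of worsening. Cohort 2 subjects have their glucocorticoid dose reduced before study drug starts, so new symptoms in that window are plausible.

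**Working it through.** The plan has no figure to reproduce here, and no power or sample-size formula applies. The check applies the recording and counting rules to two invented AE histories.

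**Inputs**
- Dose path of a non-responder (Protocol 3.1.3): 500 mg BID from Day 1, 1000 from Day 29, 1500 from Day 57, 2000 from Day 85.
- Time between consent and first dose (Protocol 3.1): shortest 2 + 2 = 4 weeks, longest 14 + 8 = 22 weeks, all approximate.
- Event days (assumptions). History A: mild from Day 20, severe from Day 60. History B: mild from Day -10, severe from Day 40.

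**Results**

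| History | Recording | Counting | Result |
|---|---|---|---|
| A | One record: start Day 20, maximum severe | Dose at start date | Severe at 500 mg BID |
| A | Two records: Day 20 mild, Day 60 severe | Lowest dose and worst severity together: min(500, 1500) = 500; worst of mild and severe = severe | Severe at 500 mg BID |
| A | Two records | Worst severity within each dose | Mild at 500, severe at 1500 mg BID |
| B | One record: start Day -10, maximum severe | Status read from start date; SAP 7.3 onset = -10 | Not treatment-emergent |
| B | New record at Day 40 | Status read from new start date | Treatment-emergent, severe, 1000 mg BID |

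**Reading the table**
- The first two rows for A agree. Splitting the record does not cure the severity-by-dose table if the lowest-dose and worst-severity rules are then applied together.
- A different counting rule does not help either if the date of worsening was not captured. Both parts are needed, as in the third row.
- For B, the result turns entirely on whether the worsening gets its own date. For an AE that first arose after consent, the documents neither require nor forbid this.

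**The case against.** **The form is not available.** A reader might infer that every AE has exactly one record and that worsening is never captured. The documents do not establish that. Protocol 6.10.2 says how to grade and SAP 7.3 gives formulas; neither is a data model, and the eCRF and its completion guidelines are not included. The request for a maximum, and the instruction in Protocol 6.10.4.2 to update the form when follow-up information arrives, point towards one record, but that is inference. What stands is that no rule is stated.

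**Some worsening is covered.** A reader might infer that worsening can never be recognised as treatment-emergent. That is too strong. Protocol 6.10.1 makes worsening of a condition present at screening reportable and treats any change in condition as an AE. SAP 7.7 includes worsening of pre-existing conditions in time to onset. The remaining gap is AEs that first arise between consent and first dose.

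**The dose rule is worded for several AEs.** SAP 7.7 does not say where one continuing AE falls, and the mock tables are not supplied. The first row for A is therefore a plausible reading, not a certain one. Where a subject has two AE records, the lowest-dose rule does apply, although the SAP does not say how it combines with the worst-severity rule.

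**Splitting records could create the opposite bias.** SAP 7.7 also plans AEs per patient-year by dose. A new record at each worsening, but not at improvement, adds counts at the later and usually higher dose. This objection is correct, and the fix has to deal with it.

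**The consequence is limited.** Safety analyses are descriptive (Protocol 9.6.2) in about 20-24 evaluable subjects. AEs and dosing are listed by subject, and SAP 7.7 also shows treatment-emergent AEs by time range. This stands in part: a listing that shows only onset date and maximum severity would not reveal the dose at which the maximum was reached. Protocol 3.2 also reports that earlier experience suggests better tolerability with longer dosing, which is a reason not to assume that worsening is frequent.

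**Conclusion.** The point holds as a gap in the recording rules combined with a counting rule that suits this design badly. Followed as written, the plan can show severity reached after an up-titration at a lower dose, and it cannot reliably derive treatment-emergent status by worsening for AEs first arising before dosing but after consent. The direction favours the higher doses.

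No size can be given. The documents do not say how many AEs start at one dose and worsen at another, and any count of affected subjects would be invented; the two histories only show the mechanism. The longest pre-dose window, 22 weeks, is an extreme that Protocol 6.1 allows with Medical Monitor approval, for example for Cohort 2 glucocorticoid adjustment.

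The conclusion assumes that the eCRF guidelines add no rule on worsening and that the mock tables apply the two counting rules together. If either assumption is wrong, the corresponding part of the problem is smaller. For AEs that start after first dose, maximum severity over all doses combined is unaffected. The primary efficacy endpoint is unaffected too.

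**What to change.** 1. **Protocol 6.10.2 and eCRF guidelines.** When severity increases after the first dose or after a dose change, enter a linked AE record with its own start date and severity, or a dated severity change on the existing record.
2. **SAP 7.7, definition.** Restate the treatment-emergent definition, including worsening, and say that it uses the date of the linked record or severity change.
3. **SAP 7.7, Tables 14.3.1.4 and 14.3.1.6.** Count each subject's worst severity within each dose, attributed to the dose being taken when that severity was reached, in place of the lowest-dose and worst-severity rules together.
4. **SAP 7.7, incidence and rates.** Collapse linked records into one event for subject-level incidence and for AEs per patient-year, so that splitting does not inflate counts at later doses.

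The cost is slightly more data entry and some programming. Dates of worsening are best collected as they occur; for AEs already entered, they would have to be sought from source records by query before database lock.
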